## 9.5 MISSING DATA

To compare the proportion of participants that achieve the serum 25(OH)D levels greater than 40 ng/ml target among the standard of care group and the optimal PK dose group, differences in sample proportions will be evaluated by chi-square or Fisher's exact test as appropriate. Additionally, proportion difference with the 95% confidence interval will be obtained.

Participants will be defined as a responder or non-responder at the 16-week visit according to the serum level criteria (i.e., achieve a serum 25(OH)D of greater than or equal to 40 ng/ml at 16 weeks). Participants who withdraw prematurely will be considered non-responders in the primary analysis.

To investigate the effect of missing data on the proportion of response endpoint, a sensitivity analysis will be carried out using a multiple imputation approach. Additionally, all participants who do not complete the recommended 16-weeks dosing regimen will be regarded be excluded from the per-protocol analysis population.

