### 6.3 MEASURES TO MINIMIZE BIAS: RANDOMIZATION AND BLINDING

#### Randomization

Randomization of participants will be done online using the randomization module of the DCOC electronic data capture system. For the first part of the study, participants were randomized using a 1:1:1:1 ratio to receive 1 of 4 dose regimens after providing consent and confirmation of eligibility on the study inclusion and exclusion criteria. Upon completion of the interim PK analysis, participants in the second part will be randomized using a 2:1 ratio to receive the treatment regimen or the SoC comparator. The randomization will use a stratified block scheme. Stratification will be by age (6-11 vs 12- less than 18 years of age) and BMI age and sex percentile at entrance (overweight = greater than or equal to 85th% to less than 95th% BMI, obese = greater than or equal to 95th% BMI for age and sex, and obese = greater than or equal to 99th% BMI for age and sex).

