### 9.2 SAMPLE SIZE DETERMINATION

Part 1: a sample size of greater than 50 participants will be powered (greater than 80%) to target a 95% confidence interval within 60% and 140% of the geometric mean estimates of 25(OH)D systemic clearance. The sample size assumes a coefficient of variation of 50% in 25(OH)D steady-state concentration.(48, 89) Based on prior experience (90, 91, 92, 93) a sample size of 16 participants in the interim analysis will suffice to determine a recommended dose for Part 2.

Part 2: For the optimal dosing regimen defined by the interim PK-analysis, the null hypothesis that the proportion of children who achieve a vitamin D level of greater than or equal to 40 ng/ml is 50% or less at 16 weeks will be tested against the alternative hypothesis that the proportion is 75% or more at the one-sided 0.05 significance level with power of 0.90. Using the one group Chi-square test for testing a single proportion, the number of study participants required to complete Part 2 is 31 participants. To allow for an approximately 30% dropout rate (due, in part, to the COVID-19 pandemic), 63 participants will be randomized to (A) the 8,000 IU daily dose (with a 50,000 IU loading dose) regimen or to (B) the standard of care (600 IU/day) dose. The allocation ratio will be 2:1 (A:B).

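### The exploratory comparison of recommended dose with standard of care uses a cut-off that contradicts the endpoint and ignores the randomization strata; both are cheap to fix and the expected effect is small

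*Combined protocol and SAP*

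**What the plan says.** **Randomization (section 6.3).** Blocks are stratified: "Stratification will be by age (6-11 vs 12- less than 18 years of age) and BMI age and sex percentile at entrance". Two age groups and three BMI classes give six strata.

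**The comparison (section 9.5).** For the SoC group against the optimal-dose group, "differences in sample proportions will be evaluated by chi-square or Fisher's exact test as appropriate", and a difference with a 95% interval is added. No stratification, significance level, sidedness or visit is given. The target is written as "serum 25(OH)D levels greater than 40 ng/ml target".

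**The responder rule (section 9.5, next paragraph).** A responder has 40 ng/ml or above at 16 weeks. The Part 2 endpoint and exploratory endpoint 5 (sections 1 and 3) also use 40 or above.

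**Status.** The comparison serves exploratory objective 3. The powered Part 2 analysis is a one-group test of the active cohort (sections 9.1, 9.2 and 9.4.4): the null is that the proportion "is 50% or less at 16 weeks", against "the alternative hypothesis that the proportion is 75% or more", at the "one-sided 0.05 significance level with power of 0.90".

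**Comparator.** Section 9.5 speaks of the standard-of-care group without naming Cohort B. Part 1 also had a 600 IU/day arm (Cohort 4).

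**The concern.** Three details of one comparison do not match the rest of the plan.

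- A child recorded at exactly 40 ng/ml is a responder for the Part 2 endpoint but not for the between-group comparison, so the same cohort could be reported with two response rates.
- Stratified blocks remove part of the chance variation between arms. An unstratified standard error does not credit this, so if age and BMI predict response the interval is somewhat too wide and the test somewhat conservative.
- The comparator is open to two readings: Cohort B alone, or Cohort B plus earlier Part 1 children on the same dose.

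At stake is the clarity and calibration of an exploratory estimate whose stated purpose is to show that any rise in the active cohort is not due only to unmeasured factors.

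**Working it through.** **1. The plan's own figure.** One-group test, p0 = 0.50, p1 = 0.75, one-sided 0.05, power 0.90:

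n = [(1.645 × √(0.5 × 0.5) + 1.282 × √(0.75 × 0.25)) / 0.25]² = 30.35, rounded up to 31.

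This matches: "the number of study participants required to complete Part 2 is 31 participants". The test has no between-arm contrast, so nothing below touches it.

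**2. The cut-off.** Above 40 and 40-or-above differ only for results recorded as exactly 40. Assume week-16 values in Cohort A are roughly normal with mean 48-55 and SD 12-20 ng/ml. The density at 40 is then 0.015 to 0.027 per ng/ml. Results in whole ng/ml put 1.5% to 2.7% of children at exactly 40, at most 0.027 × 42 = 1.1 children. Results to 0.1 ng/ml put about 0.2% to 0.3% there. One child is 1/42 = 2.4 percentage points.

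**3. Standard error by formula.** 63 randomized at 2:1 gives 42 v 21. The SoC response rate is not stated. Section 4.3 reports a mean rise of 12.4 (SD 9.7) ng/ml on 1000 IU/day in obese adults. From a baseline of about 20 that puts about 22% at 40 or above, and linear scaling to 600 IU about 10%. I use 5% and 20%.

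Unstratified at 75% v 5%: SE = √(0.75 × 0.25/42 + 0.05 × 0.95/21) = √(0.004464 + 0.002262) = 0.0820.

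With stratum rates in Cohort A of variance V, the first term becomes (0.1875 − V)/42. For six equal strata with evenly spaced rates, V = d² × 35/12, where d is the step between strata:

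| Range across strata in A | d | V | Stratified SE | Reduction |
|---|---|---|---|---|
| 85% to 65% | 0.04 | 0.0047 | 0.0813 | 0.8% |
| 90% to 60% | 0.06 | 0.0105 | 0.0805 | 1.9% |
| 95% to 55% | 0.08 | 0.0187 | 0.0793 | 3.4% |

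**4. What the documents suggest about BMI.** Section 2.2 gives levels 8 ng/ml lower in obese and 3.2 lower in overweight participants than in those of normal weight, a gap of 4.8. With the section 4.3 SDs of 10.2 to 19.6 and a mean response of 75% (normal values assumed), response differs by about 8 to 15 points between the two classes. With two equal strata the SE falls by 0.3% to 1%. This leaves out age and the class at or above the 99th percentile.

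**5. Simulation.** 8,000 trials per scenario, 2:1 blocks of 3 within six strata (age 50/50, BMI 25/45/30, assumed), two-sided 0.05 (assumed). Moderate means an odds ratio of 2 per BMI step and for age; extreme means 4. Withdrawals counted as non-responders turn 75% into 0.75 × 0.70 = 52.5%, using the plan's "approximately 30% dropout rate".

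| A v B | Stratum effect | Power, Pearson / CMH | SD of difference, unstratified / MH | Nominal SE ÷ unstratified SD |
|---|---|---|---|---|
| 75% v 5% | none | 100% / 100% | 0.0800 / 0.0806 | 0.0820/0.0800 = 1.025 |
| 75% v 5% | moderate | 100% / 100% | 0.0819 / 0.0822 | 0.0820/0.0819 = 1.001 |
| 75% v 5% | extreme | 100% / 100% | 0.0781 / 0.0782 | 0.0820/0.0781 = 1.050 |
| 52.5% v 20% | none | 73.3% / 71.7% | 0.1167 / 0.1170 | 0.1164/0.1167 = 0.997 |
| 52.5% v 20% | moderate | 74.9% / 76.3% | 0.1116 / 0.1118 | 0.1164/0.1116 = 1.043 |
| 52.5% v 20% | extreme | 75.2% / 81.9% | 0.1056 / 0.1049 | 0.1164/0.1056 = 1.102 |

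The first row should be 1, so departures of about 2% are simulation noise. The spread of the estimate is nearly the same either way, because the blocks already balance the arms. Only the reported SE is affected, and in the safe direction: at 30% v 30%, Pearson type I error was 5.2%, 4.2% and 3.0% for no, moderate and extreme effects, against 5.0%, 5.1% and 5.0% for CMH.

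**The case against.** The best defence is that this hardly matters. The comparison is exploratory and carries no stated power. The unstratified test already has about 99% power or more at 75% v 5% to 20%. Six strata leave 21/6 = 3.5 SoC children each, and at a 5% response about one SoC responder in all (21 × 0.05), so a stratified analysis can be unstable and can lose a little power when the strata do not matter. Section 9.4.1 also defers detail to a separate SAP, which is not in the text available to me; whether it stratifies cannot be shown. All of this stands. It limits the size of the point but does not remove the conflicting cut-off or the unnamed comparator.

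Several stronger readings are tempting and not supported:

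- **A material loss of precision.** A reader might infer SE ratios of 0.979, 0.950 and 0.917, worth 4% to 19% more children (1/0.979² to 1/0.917²). Those figures need two equal strata and SoC response that also varies by 3 to 5 points either way. The design has six strata.
- **The cut-off costs precision.** It does not; it is a conflict of definition.
- **The strata were chosen because a fixed dose acts differently by body size.** Section 6.3 gives no reason for them. Section 2.2 makes BMI plausibly prognostic, which is a weaker statement.
- **Part 1 SoC children will be pooled in.** The text does not say so. It also does not exclude it.

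**Conclusion.** The point holds in a limited form. The contradiction over the cut-off is certain from the text and affects at most about one child of 42 on the assumed distributions. The mismatch between stratified randomization and an unstratified test and interval is real as section 9.5 is written, but its effect is a slightly conservative SE: about 0-3% at 75% v 5% for response ranges up to 40 points over six strata, about 5% in simulation with extreme effects, and about 10% only with extreme effects and arms at 52.5% v 20%. The largest power difference seen was 81.9% v 75.2%, in that last case. These sizes rest on assumed SoC rates, stratum sizes, stratum effects and a two-sided 5% level, none of which the documents state. A reader should not infer any threat to the Part 2 conclusion: the one-group test and its 31 completers do not depend on this comparison.

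**What to change.** In section 9.5, and in the SAP if it is not already there:

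1. Define response for this comparison as 40 ng/ml or above at 16 weeks, as in the responder paragraph.
2. Name the concurrently randomized Cohort B as comparator. If Part 1 SoC children are wanted, make that a separate, labelled analysis.
3. Report the Mantel-Haenszel risk difference with a stratified 95% interval, and a Cochran-Mantel-Haenszel test (exact if sparse), by the randomization factors.
4. State beforehand how BMI classes are merged, for example to two levels when a stratum is empty in either arm.
5. Report the unstratified difference, interval and test alongside, and state the significance level and sidedness.

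The cost is a few sentences, with no change to sample size, visits or data collection. The downside is slight instability in sparse strata, which items 4 and 5 contain. Items 1 and 2 are worth making whatever view is taken of item 3.

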	
Exploratory endpoints:
 

1. Inflammatory biomarker panel to include serum leptin as well as tumor necrosis factor alpha (TNF<math>\alpha</math>), interleukin-2 (IL-2), IL-6, IL-10 and IL-17 (cytokine panel)

2. Asthma exacerbations

3. Asthma Symptom Days (ASDs)

4. Asthma Control Test (ACT) (or Childhood Asthma Control Test [c-ACT] for participants less than 12 years of age)

5. Differences in the proportion of participants that achieve serum 25(OH)D levels greater than or equal to 40 ng/ml

Study Population:	Approximately 107 participants randomized (321 enrolled), ages 6 to less than 18 years of age at enrollment, body mass index (BMI) greater than or equal to 85% for age and sex, with physician-diagnosed asthma and baseline serum 25(OH)D level less than 30 ng/ml and greater than 10 ng/ml
Phase:	PK / dose finding study
Description of Sites/Facilities Enrolling Participants:	Open to sites of the IDeA States Pediatric Clinical Trials Network (ISPCTN)
Description of Study Intervention:	
Part 1: (Dose Finding)
 
A total of 50 participants were randomized (1:1:1:1) into one of four 16-week vitamin D3 oral regimens:
 
Cohort 1: Single 50,000 IU loading dose + 6000 IU daily dose
 
Cohort 2: Single 50,000 IU loading dose + 10,000 IU daily dose
 
Cohort 3: 6000 IU daily dose
 
Cohort 4: 600 IU daily dose (standard of care comparator [SoC] group)
 
After a minimum of 16 participants (4 in each group) completed PK sampling at Week 20, we performed an interim analysis to determine the recommended dose for use in Cohort A for Part 2 of the study.
 
Part 2: (Dose Confirming)
 
Up to 63 additional participants will be randomized into one of two 16-week vitamin D3 oral regimens in a 2:1 ratio:
 
Cohort A: Single 50,000 IU loading dose + 8,000 IU daily dose
 
Cohort B: 600 IU daily dose (SoC)

Study Duration:	42 months Part 1: 17 months (assumes 6 randomizations/month) Interim Analysis period: 2 months Part 2: 17 months (assumes 6 randomizations/month) Final Analysis period: 6 months

Title: Vitamin D Oral Replacement in Asthma

Sponsor: ISPCTN DCOC

Participant Duration:	30 weeks (2-week screening/run-in, 16-week intervention, 12-week follow-up period)
------------------------------	--

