## Retention

Similar to recruitment, retention tactics should be tailored to the individual resources and challenges of each site. These include the study being too long or burdensome, the participant feeling they are not benefitting from participation, unengaged or unenthusiastic study staff, and lack of physician involvement and attention. The study staff must recognize that the study participants (and caregivers) are providing a service to the study while undergoing risk and participants must feel appreciated.

The target for completion is 80% of randomized participants.

More details about recruitment and retention processes can be found in the Recruitment and Retention Plan in the Manual Operating Procedures (MOP), including detailed descriptions of best practices, strategies to be implemented, and metrics to be monitored.

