To ensure safety in this study, spot urine calcium/creatinine levels will be measured at each visit as a screen for hypercalciuria. The study coordinator will instruct the participant and his or her parent, legal guardian, or caregiver to ensure that the child is well-hydrated prior to the study visit. If the urine calcium/creatinine level is greater than 0.37 on a specimen, the participant will be asked again to ensure good hydration and return within 2 business days for a repeat spot urine calcium/creatinine measurement. If the ratio remains greater than 0.37, then a serum calcium level and 25(OH)D for the local laboratory will be obtained.(75) If serum calcium is greater than  $1.5 \times \text{ULN}$  or the 25(OH)D level is greater than 100 ng/ml, the participant will have supplementation stopped but will be asked to return for remaining study visits in order to obtain data on vitamin D clearance and for safety assessments. Vitamin D supplementation ends at 16 weeks (day  $112 \pm 7$ ) for all participants. They will be followed for another twelve weeks for determination of elimination kinetics and for safety assessments. The half-life of vitamin D is variable but is felt to be approximately 2 months.(88) The 12-week follow-up therefore consists of 1.5 half-lives. A serum 25(OH)D level will be drawn for the local laboratory safety measure at week 28 (visit 9; day  $196 \pm 7$ ). If a participant has a serum 25(OH)D level greater than 80 ng/ml at that time, he/she will be asked to return 4 weeks later for a re-check to ensure that the level is not continuing to rise as vitamin D washes out of adipose tissue. If there are any ongoing concerns, further follow up will be determined by the local investigator in collaboration with the child's primary care team and sub-specialists as necessary.

This is not an asthma treatment study. We will monitor asthma symptoms, however. Each participant is required to have an identified asthma-care provider at entry. This can be a specialist or a primary care provider. If it is found that a participant's asthma is poorly controlled, he or she will be referred back to the primary asthma-care provider for reevaluation and further treatment.

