### 9.4.2 ANALYSIS OF THE STUDY ENDPOINT

The study does not include an efficacy endpoint. The primary objective is to conduct a population PK analysis.

A population PK analysis will be performed to characterize the PK of vitamin D in overweight/obese children using the software Nonlinear Mixed Effects Modeling (NONMEM, version 7.2). Different structural PK models (e.g., 1 and 2 compartment) with linear or non-linear (e.g., Michaelis-Menten) kinetics will be fitted to the concentration-time data of 25(OH)D. Between-participant variability on model parameters and different residual error models will be tested. Model development will be guided by goodness of fit plots, plausibility of parameter estimates, and reduction in inter-individual variability for structural and residual error parameters, as well as objective function and shrinkage values.

Covariate evaluation will be performed to examine the relationship between model parameters and demographic factors (e.g., age, weight status, ethnicity) and co-administered medications, as applicable. More detail about the weight status measures used in the model will be included in the SAP. Appropriate covariates will be incorporated into the model using a standard forward inclusion-backward elimination approach. Standard model diagnostic plots and procedures will be used to evaluate model appropriateness. Model validation will be performed using visual predictive check and bootstrapping.

Using the final PK model and parameter estimates, serum concentration-time profiles of 25(OH)D will be simulated for each participant at varied dosing regimens. The percentage of participants with serum 25(OH)D greater than or equal to 40 ng/ml during a desired time period will be calculated. The best dosing regimen will be determined as the one resulted in serum 25(OH)D greater than or equal to 40 ng/ml in a majority (i.e.

75%) of participants. It is possible that the doses outlined and evaluated in this study will not end up being the dose chosen for a larger randomized, controlled, double-masked intervention trial. Creation of a PK model will determine the optimal dosing strategy in Part 2 to achieve serum vitamin D levels greater than or equal to 40 ng/ml.

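### The 0.90 power for Part 2 assumes dropouts leave the denominator, but the primary analysis counts them as non-responders; if 75% is the rate among children measured at Week 16, power drops below 0.90 at about 4–5% early withdrawal.

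*Combined protocol and SAP*

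**What the plan says.** Section 9.2 (Sample Size Determination) tests a null response rate of 50% or less against "the alternative hypothesis that the proportion is 75% or more at the one-sided 0.05 significance level with power of 0.90", using a one-group chi-square test, and concludes that "the number of study participants required to complete Part 2 is 31 participants". It continues: "To allow for an approximately 30% dropout rate (due, in part, to the COVID-19 pandemic), 63 participants will be randomized", allocated 2:1 to Cohort A and Cohort B.

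Section 9.5 (Missing Data) defines response as 25(OH)D of at least 40 ng/ml at 16 weeks and states: "Participants who withdraw prematurely will be considered non-responders in the primary analysis". It adds a multiple-imputation sensitivity analysis and a per-protocol set without children who did not complete 16 weeks of dosing. Section 9.3 applies the intent-to-treat population to every non-PK analysis.

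Two other statements bear on how much loss to expect. Section 5.5 (Retention) says: "The target for completion is 80% of randomized participants". Section 8.2 says of the time after dosing ends at Week 16: "They will be followed for another twelve weeks for determination of elimination kinetics and for safety assessments". Dropout over the whole study is therefore not the same as dropout before the Week 16 sample.

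**The concern.** Adding participants to offset dropout works when dropouts leave both the numerator and the denominator: the response rate stays at 75% and only n has to be protected. Under Section 9.5 dropouts stay in the denominator as failures. The tested proportion becomes 75% × (1 − d), where d is the share of Cohort A withdrawing before the Week 16 sample, and it moves toward the 50% null as d grows. Extra enrolment does not undo that in the way Section 9.2 assumes.

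The Part 2 comparison is the only hypothesis test named in Section 9.1 and the only one given a power. The dropout allowance is also the stated reason for randomizing 63. What is at stake is a false negative: a regimen that brings 75% of measured children to the target could fail its confirmatory test through attrition alone, and be read as inadequate when the later intervention trial is designed.

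**Working it through.** **Inputs.** One-sided alpha 0.05, p0 = 0.50, p1 = 0.75, power 0.90, 31 completers, 63 randomized 2:1 (Sections 9.1 and 9.2). Cohort A = 63 × 2/3 = 42 (derived). Withdrawals count as failures (Section 9.5). Assumption: 75% is the rate among children measured at Week 16.

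**1. Reproduce the plan's figure.** n = [(1.645 × √(0.5 × 0.5) + 1.282 × √(0.75 × 0.25)) / 0.25]² = 30.35, rounded up to 31. This matches Section 9.2, with no reduction of the 75% for withdrawals.

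**2. Rejection rule at n = 42.** z = (x − 21)/√10.5. At x = 26, z = 1.54; at x = 27, z = 1.85. The test rejects at 27 or more responders, with exact size 0.044.

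**3. Power under the Section 9.5 rule.** Power = P(X ≥ 27 | n = 42, p = 0.75(1 − d)).

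| Withdrawal before Week 16 (d) | Tested proportion | Exact power | Normal approximation |
|---|---|---|---|
| 0% | 0.750 | 0.958 | 0.967 |
| 5% | 0.7125 | 0.877 | 0.890 |
| 10% | 0.675 | 0.733 | 0.747 |
| 15% | 0.6375 | 0.541 | 0.557 |
| 20% | 0.600 | 0.345 | 0.361 |
| 30% | 0.525 | 0.084 | 0.093 |

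Power crosses 0.90 at d = 3.9% (exact) or 4.5% (approximation). With a fixed number of withdrawals k, P(X ≥ 27 | 42 − k, 0.75) is 0.897 for 2, 0.777 for 4, 0.588 for 6 and 0.357 for 8.

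**4. Which analysis the 0.90 describes.** Running the same test on measured children only, averaged over the number measured, gives 0.92 at 20% loss and 0.88 at 30%. The stated power fits that analysis.

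**5. Timing (illustration only; the documents give none).** If loss is spread over 28 weeks, the share falling before Week 16 is total × 16/28 (linear) or 1 − (1 − total)^(16/28) (constant hazard).

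- Total 30%: 17.1% or 18.4% before Week 16; power 0.455 or 0.404.
- Total 20%, which is what the completion target implies: 11.4% or 12.0%; power 0.681 or 0.661.

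**6. Restoring 0.90 by size alone.** The Section 9.2 formula with p1 = 0.75(1 − d) gives Cohort A of 44 at d = 5%, 67 at 10%, 110 at 15% and 211 at 20%.

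**7. The other reading of 75%.** If 75% already counts withdrawals as failures, 42 children give exact power 0.96. The rate among measured children would then have to be 0.75/0.90 = 83% at 10% loss and 0.75/0.80 = 94% at 20%. At 30% it would be 0.75/0.70 = 107%, which is impossible.

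**The case against.** The strongest case against is one of importance, and several parts of it are true.

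- Section 9.4.2 says "The primary objective is to conduct a population PK analysis", and anyone with one PK sample enters that analysis. Counting withdrawals as failures is also conservative: it does not inflate the type I error.
- Only withdrawal before Week 16 matters. Stopping study drug is not withdrawal (Section 7.1), and children who stop are asked to attend their remaining visits. Early loss may therefore be well below 30%.
- The alternative is 75% or more. With 80% response among measured children, power is 0.97 at 5% loss and 0.898 at 10%.
- The plan's 0.90 is a normal-approximation figure; exact power at 31 completers is 0.872. Compared exact with exact, the crossing is about 5.2% rather than 3.9%.
- Section 9.5 does not name the Part 2 test when it speaks of the primary analysis.

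These points limit how large the shortfall will be in practice, but they do not remove the mismatch. Planned power is properly quoted at the stated 75%. The crossing lies at about 4–5% by whichever convention. The responder definition in Section 9.5 is the Part 2 endpoint. Even the even-spread illustration at the plan's own 80% completion target leaves power below 0.70.

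**Conclusion.** The concern holds. Sections 9.2 and 9.5 describe different analyses, and the 0.90 belongs to the one that is not primary. The sizes above rest on three assumptions: Cohort A of 42, 75% response among children measured at Week 16, and d counting only withdrawals before that sample. The result does not depend on exactly 42: for Cohort A of 40 to 44, power is 0.70–0.80 at 10% loss and 0.32–0.42 at 20%. If the sponsor intended 75% of all children randomized to Cohort A, power is adequate, but the dropout allowance then has no purpose and Section 9.2 needs to say what was meant. The PK objective is unaffected.

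**What to change.** Keep the non-responder rule as primary and align Section 9.2 with it.

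1. In Section 9.2, replace the 0.90 statement with wording such as: *Withdrawals before the Week 16 sample count as non-responders (Section 9.5). With 42 participants in Cohort A and 75% response among those measured at Week 16, power is 0.96, 0.88, 0.73, 0.54, 0.34 and 0.08 at 0, 5, 10, 15, 20 and 30% withdrawal before Week 16.*
2. State whether 75% refers to children measured at Week 16 or to all randomized to Cohort A, and how much of the 30% is expected before Week 16.
3. In Section 9.5 and the SAP, say explicitly that the rule governs the Part 2 test. Beside multiple imputation, add the proportion at or above 40 ng/ml among Cohort A children with a Week 16 central-laboratory value, including those who stopped drug but stayed in the study. This overlaps partly with the per-protocol set, but that set drops children who were off drug yet measured.

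The cost is wording and one additional analysis, with no change to the primary rule or to the 63 participants. The drawback is a less favourable stated power. Recovering 0.90 through enrolment alone would take about 67 in Cohort A at 10% early loss, or about 211 at 20%.
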